#### **5.2.3. Analyses for Categorical Endpoints**

Categorical endpoints will be summarized by treatment and visit (if appropriate) with number and percent of participants in the treatment group within each category, if not otherwise specified.

## **5.3. Methods to Manage Missing Data**

### **5.3.1. Safety Data**

For the analysis of safety endpoints, the sponsor data standard rules for imputation will be applied.

### **5.3.2. Pharmacokinetic Data**

#### **Concentrations Below the Limit of Quantification**

In all data presentations (except listings), concentrations below the limit of quantification (BLQ) will be set to zero. (In listings BLQ values will be reported as “<LLQ”, where LLQ will be replaced with the value for the lower limit of quantification.)

## **Deviations, Missing Concentrations and Anomalous Values**

In summary tables, plots of mean profiles and plots of median profiles, summary statistics will be calculated setting concentrations to missing if one of the following cases is true:

1. A concentration has been collected as ND (ie, not done) or NS (ie, no sample);
2. A deviation in sampling time is of sufficient concern or a concentration has been flagged anomalous by the pharmacokineticist.

Note that summary statistics will not be presented at a particular time point if more than 50% of the data are missing.

## **Pharmacokinetic Parameters**

Actual PK sampling times will be used in the derivation of PK parameters.

If a PK parameter cannot be derived from a participant's concentration data, the parameter will be coded as NC (ie, not calculated). (Note that NC values will not be generated beyond the day that a participant discontinues.)

In summary tables, statistics will be calculated by setting NC values to missing; and statistics will be presented for a particular dose with  $\geq 3$  evaluable measurements.

If an individual participant has a known biased estimate of a PK parameter (eg, due to known loss of drug during subcutaneous administration), this will be footnoted in summary tables and will not be included in the calculation of summary statistics.

### **5.3.3. Pharmacodynamic Data**

Missing values will not be imputed.

## **6. ANALYSES AND SUMMARIES**

### **6.1. Primary Endpoint(s)**

To assess the pharmacokinetics of vupanorsen, the PK parameters detailed in [Section 3.1](#) will be listed, summarized and plotted by treatment (vupanorsen 80 mg and 160 mg) for participants in the PK parameter analysis set (as defined in [Section 4](#)). Missing values will be handled as detailed in [Section 5.3.2](#). Each PK parameter will be summarized by treatment and will include the set of summary statistics as specified in the table below:

**Table 3. PK Parameters to be Summarized Descriptively by Treatment**

Parameter	Summary Statistics
$C_{max}$ , $AUC_{24h}$ , $AUC_{48h}$ , $AUC_{last}$ , $AUC_{inf}$ , $CL/F$ , $V_z/F$	n, arithmetic mean, median, SD, minimum, maximum, percent coefficient of variation (%CV), geometric mean and geometric %CV
$T_{max}$	n, median, minimum, maximum
$t_{1/2}$	n, arithmetic mean, median, %CV, SD, minimum, maximum

There will be one summary table presenting all PK parameters.

To assess the relationship between the PK parameters and dose, box and whisker plot of dose normalized  $C_{max}$ ,  $AUC_{24h}$ ,  $AUC_{48h}$ ,  $AUC_{last}$ , and  $AUC_{inf}$  will be plotted against dose, and will include individual participant values and geometric means for each dose. Geometric means will have a different symbol than individual values. The values will be dose normalized (to 1 mg dose) by dividing the individual values and raw geometric means by dose. A footnote will be added to the plots to indicate that geometric means are presented.

The PK concentrations will be listed and summarized for participants in the PK concentration analysis set. Presentations for PK concentrations will include:

- A listing of all concentrations sorted by subject ID, treatment and nominal time postdose. The concentration listing will also include the actual times. Deviations from the nominal time will be given in a separate listing. The listing will be paged by treatment.
- A summary of concentrations by treatment and nominal time postdose, where the set of statistics will include n, mean, median, standard deviation, coefficient of variation (cv), minimum, maximum and the number of concentrations above the lower limit of quantification.
- Median concentrations time plots (on both linear and semi-log scales) against nominal time post dose by treatment (all treatments on the same plot per scale, based on the summary of concentrations by treatment and time postdose).
- Mean concentrations time plots (on both linear and semi-log scales) against nominal time post dose by treatment (all treatments on the same plot per scale, based on the summary of concentrations by treatment and time postdose).
- Individual concentration time plots by treatment (on both linear and semi-log scales) against actual time postdose. There will be separate spaghetti plots for each treatment per scale.

The length of time used for the x-axes of these plots will be decided on review of the data and will depend on how long vupanorsen concentration is quantifiable in the matrix.

For summary statistics, median and mean plots by sampling time, the nominal PK sampling time will be used, for individual subject plots by time, the actual PK sampling time will be used. For pre-dose, the actual PK sampling time will be set to 0 hour.

## **6.2. Secondary Endpoint(s)**

### **6.2.1. Safety Endpoints**

The details of safety analyses are described in the [Section 6.6](#).

### **6.2.2. Pharmacodynamic Endpoints**

The PD analysis will be conducted in the PD analysis set (as defined in [Section 4](#)). Non-fasting results will not be included in the analysis.

The baseline, the actual values, changes and percent changes from baseline in the following endpoints will be summarized by treatment and visit using descriptive statistics.

- ANGPTL3, TC, LDL-C, HDL-C, non-HDL-C, VLDL-C, TG, ApoA-I, ApoB total (including ApoB-48, ApoB-100), and ApoC-III.

Additionally, the following graphical summaries will be provided for the actual values, changes and the percent changes from baseline over time:

- Mean  $\pm$  SD by treatment and day (all treatments on the same plot);
- Individual plots against day (there will be separate plots for each treatment).

A listing for the actual values, changes and percent changes from baseline with fasting status sorted by treatment, subject ID and day will be presented.

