- d. Lipid panel should be obtained with participants in a fasted state (\geq 10-hour fasting as mentioned in [Section 5.3.1](#)). Lipid panel includes TG, non-HDL-C, direct LDL-C, TC, HDL-C, direct VLDL-C.
- e. Extended lipoprotein panel should be obtained with participants in a fasted state (\geq 10-hour fasting as mentioned [Section 5.3.1](#)). Extended lipoprotein panel includes ApoB, ApoB-48, ApoB-100, ApoC-III, and ApoA-I.
- f. Pre-dose.
- g. FSH in females amenorrhoic \geq 12 months, only.
- h. Pre-dose and 4 hours post dose.
- i. Participants should be monitored for a minimum of 2 hours after administration of vupanorsen to assess injection site reaction.
- j. Refer to Pharmacokinetic Sampling Timepoints.

Pharmacokinetic Sampling Timepoints

Visit Identifier	Single Dose and Post-Treatment Evaluation																
Study Day	1								2	3	8	15	30	60	90		
Hours Before/After Dose	0 ^a	0.5	1	1.5	2	3	4	6	8	12	24	48	-	-	-	-	-
Sampling Window	-	±10%	±10%	±10%	±10%	±10%	±10%	±10%	±10%	±1 hr	±1 hr	±1 hr	±1 day	±2 days	±2 days	±2 days	±5 days
Study intervention administration	X																
PK blood sampling	X	X	X	X	X	X	X	X	X	X	X	X	X	X	X	X	

a. Pre-dose sample collection.

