### **3.2.2. Pharmacodynamics Endpoints**

PD endpoints are:

- Percentage change from baseline in ANGPTL3 on Day 2, Day 3, Day 8, Day 15, Day 30, Day 60 and Day 90;
- Percentage changes from baseline in Lipid Panel on Day 2, Day 3, Day 8, Day 15, Day 30, Day 60 and Day 90, including fasting TG, LDL-C, HDL-C, VLDL-C, non-HDL-C, and TC;
- Percentage changes from baseline in ApoA-I, ApoB total (including ApoB-48, ApoB-100), and ApoC-III on Day 15, Day 60 and Day 90.

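### Does the SAP's exclusion of non-fasting results wrongly discard ANGPTL3 values that the protocol never required to be fasted?

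*SAP*

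**What the plan says.** SAP 6.2.2 opens by placing the PD analysis in the PD analysis set and then states that "Non-fasting results will not be included in the analysis". The endpoints to be summarised follow in one list that begins "ANGPTL3, TC, LDL-C, HDL-C, non-HDL-C, VLDL-C, TG" and goes on to the apolipoproteins. The same section plans a listing of actual values, changes and "percent changes from baseline with fasting status sorted by treatment, subject ID and day".

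SAP 3.2.2 defines the ANGPTL3 endpoint as "Percentage change from baseline in ANGPTL3 on Day 2, Day 3, Day 8, Day 15, Day 30, Day 60 and Day 90", with no mention of fasting. The lipid endpoint in the same section does mention it: "including fasting TG, LDL-C, HDL-C, VLDL-C, non-HDL-C, and TC".

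In the protocol, footnote d of the Schedule of Activities (Section 1.3) says "Lipid panel should be obtained with participants in a fasted state", and footnote e says "Extended lipoprotein panel should be obtained with participants in a fasted state". Footnote e also gives the panel's contents: "Extended lipoprotein panel includes ApoB, ApoB-48, ApoB-100, ApoC-III, and ApoA-I". ANGPTL3 is not among them. It has its own row in the schedule, and that row carries no fasting footnote. Protocol 8.6 likewise describes the ANGPTL3 serum sample without a fasting condition and attaches the fasted state to the lipids and apolipoproteins.

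**The concern.** The exclusion is worded for the PD analysis as a whole, and ANGPTL3 is part of that analysis. A programmer who applied one fasting filter to every listed analyte would be following the text, and one who filtered only the lipids and apolipoproteins could also claim to be following it. If any non-fasting sample existed, the two would produce different ANGPTL3 tables from the same data.

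ANGPTL3 is the marker that Protocol 4.2 uses to confirm target engagement. With 8 to 9 participants per dose, one lost value is a visible share of a summary cell, and SAP 5.3.3 rules out imputation of PD data. Nothing in the SAP says that a fasting condition was meant to be added for ANGPTL3 or explains why it would be.

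**Working it through.** The plan states no figure on this point, so there is none to reproduce. The check is how often the two readings can differ, and by how much.

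**When can they differ?** Inputs are the rows of the Schedule of Activities (Protocol 1.3) and the fasting rule in Protocol 5.3.1.

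| Sample | Scheduled draws | Fast required |
|---|---|---|
| ANGPTL3 | Day 1 pre-dose; Days 2, 3, 8, 15, 30, 60, 90 (8 draws) | none stated for this sample |
| Lipid panel | Screening; Day 1 pre-dose; the same 7 post-dose days | at least 10 hours |
| Safety laboratory | Screening; Day -1; the same 7 post-dose days | at least 10 hours |

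- 8 of 8 ANGPTL3 draws share a visit with a fasted lipid panel.
- 7 of 7 post-dose ANGPTL3 draws also share a visit with a fasted safety laboratory.
- 3 of the 8 draws (Day 1 pre-dose, Day 2, Day 3) fall within confinement in the research unit, where meals are easier to control.

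A non-fasting ANGPTL3 value can therefore arise only if a participant breaks a fast already required at that visit. If no fast is broken, the two readings give identical tables.

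**Size under the literal reading, post-dose breach.** Inputs are 9 enrolled and about 8 evaluable per cohort (Protocol 9.2) and 7 post-dose visits.

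- Share of one dose-by-visit cell: 1/9 = 11.1%; 1/8 = 12.5%.
- Share of all post-dose ANGPTL3 values: 7 × 18 = 126 and 7 × 16 = 112, so 1/126 = 0.8% and 1/112 = 0.9%.
- Largest possible shift in the cell mean: dropping a value at distance D from the mean of n values moves the mean by D/(n − 1). D cannot exceed SD × (n − 1)/√n. The shift is therefore at most SD/√n, which is 0.33 SD for n = 9 and 0.35 SD for n = 8. SD is that of the full cell, and one value is dropped from that cell.

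**Size under the literal reading, Day 1 pre-dose breach.** The schedule has no ANGPTL3 sample before Day 1, so an excluded pre-dose value leaves that participant with no baseline.

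- All 7 of that participant's percentage changes are lost: 7/126 = 5.6%; 7/112 = 6.3%.
- This takes 1 of 8 to 9 values from each of the 7 percentage-change cells for that dose, and the bound above applies to each cell.
- The post-dose actual values are not affected.

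**Do the documents contradict each other?** The protocol does not say that fed ANGPTL3 samples must be analysed; it only sets no fasting condition for drawing them. Protocol 9 and SAP 2 both allow the SAP to modify the planned analyses, and reserve an amendment for major changes to the primary endpoint. ANGPTL3 is secondary. A fasted-only analysis would conflict with neither document.

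**The case for a change.** The strongest case for an edit is that it would be cheap. One clause naming the analytes would remove the ambiguity and settle the rule before anyone has looked at open-label data. SAP 3.2.2 mentions fasting for lipids and not for ANGPTL3, which suggests that the broad wording of 6.2.2 was not a deliberate extension. Appendix 2 of the protocol places ANGPTL3 in a column with the apolipoproteins, but the column heading names the PD marker separately and footnote e defines the panel without it. That grouping therefore does not show that a fasted ANGPTL3 sample was intended.

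The scope is indeed unstated, and that part stands. The contrast in SAP 3.2.2 works in both directions, however. It also supports reading non-fasting results as those that failed a fasting requirement, which for PD means the two panels, and on that reading no ANGPTL3 value is lost.

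The literal reading is defensible too. It keeps every analyte at a visit in the same fasting state and avoids setting a fed value against a fasted baseline. The documents do not address any effect of food on ANGPTL3, so they give no ground for preferring one rule. The risk of a choice made after seeing the data is limited by the planned listing. A fasting-status column would have little purpose if non-fasting values were left out of it, so affected values should be visible.

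**Conclusion.** No change follows. The sentence leaves its scope open, but the gap is one that analysts can fill sensibly, and the choice is between two reasonable rules. The effect is nil unless a participant breaks a fast already required at that visit. If that happens, and the literal reading is used, the loss is 1 of 8 to 9 values in one cell for a post-dose breach, or one participant's 7 percentage changes for a breach before dosing on Day 1. The documents give no breach rate, so no expected number of lost values can be stated.

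This rests on three points: fasting is required at every visit with an ANGPTL3 draw, as the schedule shows; the endpoint is secondary and purely descriptive, and SAP 5.1 sets no hypotheses or decision rules that a shifted cell mean could affect; and the listing shows values with fasting status, as planned. Stating the scope when the tables are programmed would be tidy, but the conclusions of the study do not depend on it.

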## **6.3. Other Endpoint(s)**

Not applicable.

## **6.4. Subset Analyses**

Not applicable.

## **6.5. Baseline and Other Summaries and Analyses**

### **6.5.1. Baseline Summaries**

Demographic and baseline characteristics (age, gender, weight, height and body mass index) collected prior to the first dose of the study intervention will be summarized following the CaPS.

## 6.5.2. Study Conduct and Participant Disposition

The following participant dispositions will be reported following the sponsor reporting standards:

- A summary of participant discontinuations up to the end of study;
- Summary of participant dispositions analyzed for PK and PD, as well as for safety by treatment group;
- Summary of numbers of participant treated by treatment group.

### 6.5.3. Concomitant Medications and Nondrug Treatments

All concomitant medications as well as nondrug treatments will be provided in the listings.

## 6.6. Safety Summaries and Analyses

The safety endpoints are presented in the [Section 3.5](#). A set of summary tables split by treatment will be produced to evaluate any potential risk associated with the safety and toleration of administering vupanorsen.

No formal analyses are planned for safety data. The safety endpoints will be listed and summarized in accordance with the sponsor reporting standards, where the resulting data presentations will consist of participants from the safety analysis set.

### 6.6.1. Adverse Events

Adverse events will be listed and summarized by treatment in accordance with the sponsor reporting standards.

## 6.6.2. Laboratory Data

Laboratory data will be listed and summarized by treatment in accordance with the sponsor reporting standards. Baseline is as defined in [Section 3.5.2](#).

Incidence of laboratory test abnormalities (without regard to baseline abnormality) will be summarized by treatment based on CaPS.

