2.2.2.3.1. Safety in Healthy Participants (Study CS1)

A total of 16 participants were randomized and treated in the single dose cohorts. There were no SAEs or discontinuations due to AEs. All AEs were mild in severity. There were no AEs reported related to platelets, transaminase increases, or injection site reactions. One participant in the vupanorsen 40 mg SC group had AEs of bilirubin increased and unconjugated bilirubin increased, considered possibly related to study drug by the investigator.

A total of 32 participants were randomized and treated in the multiple dose cohorts. No deaths or SAEs were reported and no AEs or TEAEs led to study treatment discontinuation. There were no severe TEAEs; the majority of reported TEAEs were mild in severity. There were no platelet related AEs (changes in platelet counts or thrombocytopenia) and no events involving inflammation (inflammatory markers or flu-like reactions). There were no clinically relevant changes in urinalysis and or urine protein. There were 2 participants with elevated ALT in the 60 mg QW dose cohort. These changes were reversible and both

participants completed study treatment and the increase in ALT was not associated with clinical symptoms or other laboratory abnormalities. Erythema and pruritus at the injection site were reported several times for a single participant. However, no local cutaneous reactions at the injection site were reported.

There were no platelet-related AEs and no events involving inflammation (inflammatory markers or flu-like reactions). There were no clinically relevant changes in hematology (no evidence of prothrombotic effects, or significant decreases in platelet count or thrombocytopenia), urinalysis, inflammatory markers, ECG, or vital signs and no bleeding episodes reported.

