making and reporting. If QTc exceeds 450 msec, or QRS exceeds 120 msec, the ECG should be repeated 2 more times and the average of the 3 QTc or QRS values should be used to determine the participant's eligibility. Computer-interpreted ECGs should be overread by a physician experienced in reading ECGs before excluding participants.

9. Participants with **ANY** of the following abnormalities in clinical laboratory tests at screening, as assessed by the study-specific laboratory and confirmed by a single repeat test, if deemed necessary:
 - AST **or** ALT level $\geq 1.25 \times$ ULN;
 - Total bilirubin level $\geq 1.5 \times$ ULN; participants with a history of Gilbert's syndrome may have direct bilirubin measured and would be eligible for this study provided the direct bilirubin level is \leq ULN.

Other Exclusions:

10. History of alcohol abuse or binge drinking and/or any other illicit drug use or dependence within 6 months of Screening. Binge drinking is defined as a pattern of 5 (male) and 4 (female) or more alcoholic drinks in about 2 hours. As a general rule, alcohol intake should not exceed 14 units per week (1 unit = 8 ounces (240 mL) beer, 1 ounce (30 mL) of 40% spirit or 3 ounces (90 mL) of wine).
11. Blood donation (excluding plasma donations) of approximately 400 mL or more within 60 days prior to dosing.
12. History of sensitivity to heparin or heparin-induced thrombocytopenia.
13. History of substance abuse within 12 months of the screening visit.
14. Pregnant females; breastfeeding females.
15. Unwilling or unable to comply with the criteria in the Lifestyle Considerations section of this protocol.
16. Investigator site staff or Pfizer employees directly involved in the conduct of the study, site staff otherwise supervised by the investigator, and their respective family members.

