## 2.2. Study Design

This is a Phase 1, randomized, parallel-cohort, open-label study to characterize the PK, PD safety and tolerability of vupanorsen following 80 mg and 160 mg single subcutaneous dose in healthy Chinese adults with fasting triglyceride  $\geq$ 90 mg/dL. Approximately 18 participants will be enrolled in this study (N=9 for each cohort) with the goal of attaining approximately 8 evaluable participants in each cohort for a total of 16 evaluable participants.

The total duration of participation in this study is approximately 118 days, including a screening period of up to 28 days to confirm eligibility and a follow-up period of approximately 90 days. Eligible participants will progress to admission to the clinical research unit on Day -1 for a 4-day (3-night) inpatient stay. Participants enrolled will receive a single 80 mg (cohort 1) or 160 mg (cohort 2) subcutaneous dose of vupanorsen on Day 1. Following discharge on Day 3, participants will return for an on-site post-treatment evaluation on Days 8, 15, 30, 60 and 90.

Participants who discontinue prior to completion of the study for non-safety related reasons may be replaced, at the discretion of the principal investigator and sponsor study team.

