#### **3.5.2. Laboratory Data**

Safety laboratory tests will be performed as described in the protocol.

To determine if there are any clinically significant laboratory abnormalities, the hematological, clinical chemistry, urinalysis, and coagulation safety tests will be assessed against the criteria specified in the sponsor reporting standards. The assessment will not take into account whether each participant's baseline test result is within or outside the laboratory reference range for the particular laboratory parameters. Baseline will be the last predose measurement collected on Day -1.

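### The planned incidence of laboratory abnormalities ignores the Day -1 baseline, and with no placebo arm and about 9 participants per dose it cannot be read as new-onset incidence; add a baseline split or a shift table

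*SAP*

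**What the plan says.** SAP section 6.6.2 sets the counting rule: "Incidence of laboratory test abnormalities (without regard to baseline abnormality) will be summarized by treatment based on CaPS". The endpoint definition in SAP section 3.5.2 agrees with it, so this is a deliberate choice: "The assessment will not take into account whether each participant's baseline test result is within or outside the laboratory reference range". Results "will be assessed against the criteria specified in the sponsor reporting standards"; the numerical limits appear in neither document.

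A baseline is nevertheless defined in 3.5.2: "Baseline will be the last predose measurement collected on Day -1". Section 6.6.2 refers back to that definition and adds a general provision: "Laboratory data will be listed and summarized by treatment in accordance with the sponsor reporting standards". It does not say which summaries are meant.

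On design, SAP section 2.2 says: "This is a Phase 1, randomized, parallel-cohort, open-label study to characterize the PK, PD safety and tolerability of vupanorsen". The two randomized groups are 80 mg and 160 mg, with about 9 participants each and no placebo or untreated group.

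On who may enter, Protocol section 5.2, criterion 9, excludes a screening AST or ALT of 1.25 x ULN or more and a screening total bilirubin of 1.5 x ULN or more. It makes one exception: "participants with a history of Gilbert's syndrome may have direct bilirubin measured and would be eligible for this study provided" direct bilirubin does not exceed ULN.

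**The concern.** Readers usually take an incidence by treatment as the share of participants who developed the abnormality on that treatment. Under this rule it is the share with a qualifying post-dose value, whatever their value before dosing. Where there is a placebo arm, the background shows up there and can be set against the active arm. Here both arms are active, and SAP section 6.6 says the tables are meant to help judge the risk of giving vupanorsen.

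Liver tests are where this matters most. In the earlier healthy-participant study (CS1), one participant at 40 mg "had AEs of bilirubin increased and unconjugated bilirubin increased, considered possibly related to study drug by the investigator", and two at 60 mg weekly had raised ALT. The Phase 2a study (CS2) saw mean AST and ALT rise in every vupanorsen group. The 160 mg dose here is above the highest single dose, 120 mg, for which the protocol reports tolerability. A liver-test percentage that mixes old and new abnormalities is therefore hard to use.

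The SAP handles its other safety data differently. Sections 6.6.3 and 6.6.4 plan changes from baseline for vital signs and ECGs, and section 3.5.1 applies a treatment-emergent rule to adverse events. Protocol Appendix 5 also sets different liver thresholds for participants whose baseline is already raised.

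**Working it through.** The plan states no expected abnormality rate and no figure to reproduce for this table. The check has four steps.

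**1. Can an abnormal baseline enter?** Yes, from Protocol section 5.2, criterion 9:

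- AST or ALT above ULN but below 1.25 x ULN is admitted.
- Total bilirubin above ULN but below 1.5 x ULN is admitted.
- In Gilbert's syndrome, higher total bilirubin is admitted if direct bilirubin is at or below ULN; no upper limit on total bilirubin is stated.
- Other analytes have no numerical limit. They are governed by the requirement to be overtly healthy (inclusion 2) and by investigator judgment (exclusion 3).

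**2. When is such a participant counted?** Only if at least one post-dose value also meets the sponsor's criterion. The Schedule of Activities gives 7 post-dose safety laboratory visits (Days 2, 3, 8, 15, 30, 60 and 90), so there are 7 scheduled occasions. An AST or ALT that stays below 1.25 x ULN is counted only if the criterion lies below that level.

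**3. What does one such participant do to the table?** With 9 dosed per cohort:

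- one case: 1/9 = 11.1% (exact 95% CI 0.3% to 48.2%); two cases: 2/9 = 22.2%.
- If one participant carries an abnormality through and nobody develops a new one, the planned table shows 1/9 = 11.1%. Restricted to participants with a normal baseline, it shows 0/8 = 0%.

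More generally, let p be the share who meet the criterion before dosing and still meet it afterwards, and q the new-onset rate among the rest. The planned rate is p + (1 - p)q; the new-onset rate is q. With illustrative values p = 10% and q = 5%: 0.10 + 0.90 x 0.05 = 14.5%, against 5%.

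**4. How often might it happen?** The documents give no value for p, so the range below is an assumption, applied to one test. The chance of at least one carried-over case among n participants is 1 - (1 - p)^n. The last column is the exact probability that two independent binomial counts, each with n = 9, differ by 2 or more.

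| Assumed p | At least one in a cohort of 9 | At least one in all 18 | Cohorts differ by 2 or more |
|---|---|---|---|
| 2% | 16.6% | 30.5% | 2.2% |
| 5% | 37.0% | 60.3% | 9.5% |
| 10% | 61.3% | 85.0% | 21.8% |
| 20% | 86.6% | 98.2% | 36.9% |

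A difference of 2 participants is 22 percentage points between doses, with no drug effect at all. Randomization balances baseline abnormalities on average, but it does not prevent such gaps at this size.

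**The case against.** The strongest reply is that much of the plan for laboratory data lies outside the two documents. Section 6.6.2 promises summaries under sponsor standards and points to the baseline definition, which would have little purpose if no laboratory output used it. Those standards may already include change-from-baseline or shift tables. This stands: the most that can be said is that the SAP text names none. A reader might infer that laboratory baselines are ignored throughout; the documents show only that the abnormality flag ignores them.

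New problems also have another route to the report. Protocol section 8.2.4 has investigators record clinically relevant laboratory changes as adverse events, Appendix 3 includes clinically significant results that worsen from baseline, and the SAP gives adverse events a treatment-emergent rule. The CS1 bilirubin finding was itself reported as adverse events. This stands too, and it limits the harm. It does not change what the incidence table shows.

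Two further inferences are tempting and fail:

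- That every pre-dose abnormality becomes incidence under vupanorsen. It does so only if a post-dose value meets a criterion that the documents do not give.
- That a participant with Gilbert's syndrome would reproduce the CS1 unconjugated bilirubin finding in this table. Routine chemistry in Protocol Appendix 2 measures total bilirubin only; direct bilirubin is optional and tied to eligibility.

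Finally, the rule is openly stated, it over-counts and so does not hide signals, the endpoint is secondary and descriptive with no decision rule, and with about 18 participants a reader can trace Day -1 values in the listings. All of that is fair. It makes the point modest, but the printed percentage still cannot be read as new onset.

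**Conclusion.** The concern holds in a limited form. As planned, the incidence of laboratory abnormalities mixes conditions present before dosing with those that appear afterwards. No control arm shows the background, and no named companion table separates the two. Each carried-over case that still meets the criterion is worth 11 percentage points in a cohort of 9.

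The number of such cases is unknown. It depends on the sponsor's thresholds and on how common persistent abnormalities are among overtly healthy volunteers, and the documents give neither. The probabilities in the table rest on the assumed range for p, on independence between participants and on 9 dosed per cohort.

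This is an inexpensive improvement that should be made, at modest severity. It does not call safety monitoring or the primary pharmacokinetic analysis into question. If the sponsor standards already produce a baseline-aware laboratory table, naming it in section 6.6.2 settles the matter.

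**What to change.** Keep the planned table and add one of the following to SAP section 6.6.2, by treatment:

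- the incidence of post-dose abnormalities split by normal and abnormal Day -1 baseline; or
- a shift table from Day -1 to the worst post-dose value.

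Use the term new-onset only for abnormalities in participants whose Day -1 value was normal. For participants with an abnormal baseline, show the Day -1 and worst post-dose values side by side, or state in the SAP the margin that counts as worsening; the documents currently give none. Amend the sentence in section 3.5.2 to say that the baseline-blind count is accompanied by the baseline-aware one.

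The cost is SAP wording and one or two tables from data already collected, with no new samples. Protocol section 9 and SAP section 2 call for a protocol amendment only for major changes to the primary endpoint or its analysis, so none is needed here. The drawback is small cells: a cohort of 9 may split 8 and 1, and the abnormal-baseline part may amount to a listing of one person.
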